5. INTRODUCTION

SAGE-324 is a positive allosteric modulator (PAM) of A-type γ -aminobutyric acid-gated chloride channel (GABA_A) receptors, the major class of inhibitory neurotransmitter receptors in the brain. In addition to being developed as an adjunctive therapy in epilepsy and other seizure disorders under IND 139201, SAGE-324 is also being developed for the treatment of Essential Tremor (ET).

Essential tremor is a permanently debilitating, neurologically determined, common movement disorder characterized by involuntary rhythmic oscillation of a body part due to intermittent muscle contractions typically occurring when not at rest, thus interfering with fine motor skills associated with daily activities ([Olanow 2008](#), [Deuschl 2011](#), [Hopfner 2016](#), [NIH 2019](#)).

Although the pathophysiology and etiology of ET is not fully understood, it is postulated that approximately 50% of ET patients feature an autosomal dominant pattern of familial inheritance and that non-inherited cases may have toxin-based or other causality ([Olanow 2008](#), [Hopfner 2016](#)). ET is the most common movement disorder in the US, with prevalence estimated to be approximately 2.2% of the population, representing a substantial societal medical burden with over an estimated 7 million ET patients in the US alone ([Louis 2014](#)).

In general, active tasks of daily life are adversely impacted by ET, including but not limited to speech, handwriting, household tasks, and occupational demands, contributing negatively to psychosocial well-being, general anxiety, and overall quality of life ([Koller, 1989](#)). Although benign in term of its effect on life expectancy, ET is a progressive neurodegenerative condition whose symptoms are typically disabling, often forcing patients to change jobs or seek early retirement ([Zappia, 2013](#)). In some cases, serious disability may ensue.

The pharmacological profile of SAGE-324 is theorized to induce therapeutic effect in the treatment of ET. Based on preclinical studies of SAGE-324, which features a different mechanism of action than that of propranolol, the pharmacokinetic (PK)/ pharmacodynamic (PD) profile suggests SAGE-324 may safely ameliorate symptoms in patients suffering from ET, regardless of propranolol use.

There are currently ongoing Phase 1 clinical studies of SAGE-324 in healthy adults and in adults with ET. These studies, in addition to preclinical studies of SAGE-324, are detailed in the investigator's brochure.

With a GABA_A receptor-based mechanism of action featuring positive allosteric modulation capability, SAGE-324 represents a novel approach to the treatment of ET, which may help address the unmet medical need of the ET population, warranting further study of SAGE-324 as a potential treatment for this common movement disorder.

Henceforth, this double-blind, placebo-controlled efficacy and safety study of SAGE-324 will be conducted in adults and is designed to assess the effect of SAGE-324 on a variety of outcome measures specific to ET disease characteristics and associated quality of life domains.

5.1. Dose Justification

The dose of SAGE-324 planned for this study is 60 mg given as oral tablets, to be administered once daily in the morning with food. The dose was selected based on preliminary data from 3 active studies of SAGE-324, which included: unblinded data from completed cohorts in

324-CLP-101 Part A (oral solution SAGE-324 doses of 3 mg, 10 mg, 30 mg, 45 mg, 60 mg); Part C (oral solution SAGE-324 doses of 30 mg); Part D (oral suspension SAGE-324 doses of 30 mg) in healthy subjects; and preliminary data from open-label Part E (oral suspension SAGE-324 doses of 45 mg and 60 mg) in participants with ET; additional preliminary data from 324-CLP-102 cohorts 1 through 6 (cohorts 1 to 5 unblinded, cohort 6 blinded), which evaluated oral suspension doses ranging from 5 mg to 60 mg; and preliminary unblinded data from 324-CLP-104, which compared the relative bioavailability of the oral tablet (30 mg) vs oral suspension (30 mg) formulations of SAGE-324 and separately the effect of food on the PK of the SAGE-324 oral tablet. In 324-CLP-101 and 324-CLP-102 studies, doses were administered in a fasted state. The preliminary data from all of these active studies collectively informed the route of administration (oral) and dose strength of 60 mg as oral tablets planned for further evaluation in this study.

SAGE-324 was generally well-tolerated in participants with ET and in healthy volunteers, as was shown in the preliminary data of 324-CLP-101 Part E at single administration doses of 45 mg and 60 mg, and in 324-CLP-102 through once-daily administered doses of up to 60 mg for 14 days. In addition, tremor reduction was observed at both doses on TETRAS and Kinesia ONE accelerometry, with greater improvement seen at 60 mg compared to 45 mg.

In the clinically complete study 324-CLP-104, preliminary data showed that SAGE-324 oral tablets, when coadministered with a meal, resulted in exposures approximately equivalent to that of SAGE-324 oral suspension under fasted conditions. Therefore, the SAGE-324 oral tablets are recommended to be administered with food.

5.2. Benefit/Risk Assessment

Based on the mechanism of action of SAGE-324 and the results of completed nonclinical studies and preliminary data of currently ongoing clinical studies of SAGE-324, it is theorized that participants may have symptomatic amelioration, ie, tremor reduction and possibly improved quality of life from potentially stabilizing disease characteristics associated with ET.

Potential risks anticipated in this study are based on available data from toxicology studies of SAGE-324 in addition to preliminary data from 3 ongoing, currently active Phase 1 clinical studies of SAGE-324.

Available preliminary clinical data are summarized in the SAGE-324 Investigator's Brochure. There have been no deaths or SAEs related to IP, and based on the preliminary clinical data available, there have been no confirmed clinically significant trends in clinical laboratory evaluations, vital signs, or physical examinations.

Based on available preliminary clinical data from SAGE-324 active clinical studies, AEs of somnolence and feeling of relaxation are considered adverse drug reactions (ADRs). In addition to scheduled clinic visits, the current status of study participants will be reviewed via phone calls in between clinic visits, or more frequently for AE monitoring.

6. STUDY OBJECTIVES AND ENDPOINTS

Objectives	Endpoints
Primary	
To assess the effect of SAGE-324 compared to placebo on upper limb tremor reduction in individuals with essential tremor (ET) after 28 days of treatment	
Change from baseline compared to placebo in The Essential Tremor Rating Assessment (TETRAS) performance subscale part 4 upper limb tremor score on Day 29
Secondary	
To assess the effect of SAGE-324 compared to placebo on overall upper limb tremor reduction	
Change from baseline compared to placebo in TETRAS performance subscale part 4 upper limb tremor score at all other timepointsChange from baseline compared to placebo in Kinesia ONE accelerometer scores
To assess the effect of SAGE-324 compared to placebo on activities of daily living (ADLs)	
Change from baseline compared to placebo in TETRAS Scale ADL score
To assess the effect of SAGE-324 compared to placebo on overall tremor	
Change from baseline compared to placebo in TETRAS total performance score
To evaluate the safety and tolerability of SAGE-324	
Incidence of treatment-emergent adverse events (TEAEs)

7. INVESTIGATIONAL PLAN

7.1. Overall Study Design

This is a randomized, double-blind, placebo-controlled, parallel group study to evaluate the efficacy, safety, and tolerability of SAGE-324 in individuals with ET. Participants, site staff, and sponsor personnel will be masked to treatment allocation (see Section 9.5).

This study includes a Screening Period of up to 28 days, a 29-day treatment period consisting of 28 days of dosing with the end of treatment visit intended to be on Day 29 at trough, and a 14-day follow-up period relative to final dose (Figure 1). After providing informed consent, participants will undergo screening assessments as outlined in Table 2 to determine eligibility.

[figure not shown]
The Screening Period begins with the signing of the informed consent form (ICF). Eligible participants will visit the study center on Day 1 and complete additional eligibility assessments of safety and efficacy, as specified in the Schedule of Assessments (Table 2). Following completion of screening and Day 1 eligibility checks, participants will be randomized to 1 of 2 treatment groups (SAGE-324 60 mg daily, or placebo) in a 1:1 ratio.

During the double-blind Treatment Period, starting on Day 1, participants will receive a single dose of investigational product (IP) once daily in the morning with food for 28 days on an outpatient basis (see Section 10.5). Doses occurring on scheduled clinic visits will be administered in the clinic, and doses occurring on all other days will be self-administered by the participant at home as specified in Table 2. During the Treatment Period, participants will return to the study center approximately once per week for efficacy and safety assessments as specified in Table 2. If on Day 1 or at any point during the treatment period, participants experience moderate or severe AEs of somnolence, drowsiness, dizziness or similar, or experience these events at any severity with associated symptoms such as confusion or balance impairment, they must have a dose interruption (drug holiday) of at least 1 day (missing at least 1 dose). Following a drug holiday, the dose of study drug must then be reduced by 15 mg decrements to tolerability (ie, from 60 mg to 45 mg to 30 mg). The dose of IP may not be increased for the remainder of the study. At the investigator's discretion, participants unable to tolerate the 30-mg dose will be discontinued from IP. During the study, a phone call will be conducted once per week, preferably midway between clinic visits, or more frequently if deemed appropriate by the investigator, to review the current status of the participant. Details regarding dose adjustment criteria and procedures are provided in Section 7.4.

In addition to Kinesia ONE-specific training, clinical study center staff and study participants will be trained on the use of software applications and devices necessary to complete questionnaires or other assessments as required. During in-clinic visits, clinical study center staff will be available to assist participants as needed, to ensure they can access and use the software applications and devices correctly according to the training.

During the follow-up period, visits will be conducted on an outpatient basis. In addition to the phone calls to review current status, participants will receive a phone call approximately 7 days after the last dose of IP (ie, Day 35) for safety monitoring. Participants will return to the study center for an end of study visit approximately 14 days following the last dose of IP (ie, Day 42).

Figure 1: Study Design

Abbreviation: EOT = end of treatment

7.2. Number of Participants

Approximately 60 participants are planned, with approximately 30 participants enrolled per arm, to produce 25 evaluable participants per arm for primary efficacy analysis. Additional participants may be randomized if the drop-out rate is higher than anticipated (ie, >15%).

7.3. Treatment Assignment

Participants will be assigned to IP (active or placebo) in accordance with the randomization schedule on Day 1. Additional details on randomization and blinding are provided in Section 9.5.

7.4. Dose Adjustment Criteria

If a participant reports moderate or severe adverse events (as defined in Section 12.2.5) of somnolence, drowsiness, dizziness, or similar events or experiences these events at any severity with associated symptoms such as confusion or balance impairment on Day 1 or at any point during the treatment period, the participant must have a drug holiday (dose interruption) of at least 1 day (missing at least 1 dose) (Table 2). The drug holiday must be followed by reducing the dose of IP from 60 mg to 45 mg (ie, from 4 tablets of 15 mg to 3 tablets of 15 mg).

If the events persist and continue to be moderate or severe, despite the drug holiday and dose reduction, or the participant experiences a new moderate or severe AE of somnolence, drowsiness, dizziness or similar, the participant must have a further drug holiday of at least 1 day and a further dose reduction from 45 mg to 30 mg (from 3 tablets to 2 tablets).

The participant's condition must be closely monitored via phone calls or in-person visits to assess the impact of any drug holiday and dose reduction.

The reduced dose of IP will continue to be administered once daily at the same schedule as specified in the Schedule of Assessments (Table 2). The dose of IP may not be increased for the remainder of the study.

Following a second drug holiday and dose reduction to 30 mg, if the events persist or recur and are moderate or severe, the investigator must discontinue the participant from the IP. The dose may not be reduced below 30 mg.

The investigator will continue to institute drug holidays, dose reductions, or IP discontinuation over and above this minimum as clinically appropriate.

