Double-Blind Treatment Period: Starting on Day 1, participants will receive a single dose of investigational product (IP) once daily for 28 days on an outpatient basis, to be taken in the morning with food that comprises a minimum of 400 calories. Doses occurring on scheduled clinic visits will be administered in the clinic, and doses occurring on all other days will be self-administered by the participant at home. During the Treatment Period, participants will return to the study center approximately once per week for efficacy and safety assessments as specified in [Table 2](#). Participants

will be trained on the use of software applications and devices necessary to complete questionnaires or other assessments. If on Day 1 or at any point during the treatment period participants experience moderate or severe AEs of somnolence, drowsiness, dizziness or similar, or have these events at any severity with associated symptoms such as confusion or balance impairment, they must have a dose interruption (drug holiday) of at least 1 day (missing at least 1 dose). Following a drug holiday, the dose of study drug must then be reduced by 15 mg decrements to tolerability (ie, from 60 mg to 45 mg to 30 mg). The dose of IP may not be increased for the remainder of the study. At the investigator's discretion, participants unable to tolerate the 30 mg dose may be discontinued from study drug. During the study, a phone call will be conducted at least once per week, preferably midway between clinic visits, or as deemed appropriate by the investigator, to review the current status of the participant.

Follow-Up Period: Follow-up visits will be conducted on an outpatient basis. Participants will continue to complete questionnaires as indicated in [Table 2](#) and will receive a phone call approximately 7 days after the last dose of IP (ie, Day 35) for safety monitoring. Participants will return to the study center for an end of study (EOS) visit approximately 14 days following the last dose of IP (ie, Day 42).

Number of Participants (planned): Approximately 60 participants, with approximately 30 per arm.

Eligibility Criteria:

Inclusion Criteria:

1. Participant has signed an ICF before any study-specific procedures or washout of drugs is performed.
2. Participant is ambulatory and is 18 to 80 years of age, inclusive, at the time informed consent is obtained.
3. Participant has a diagnosis of ET, as defined by all of the following criteria:

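### The rule for stopping investigational product at 30 mg for sedation-type events is stated at conflicting strengths in the Synopsis, Section 7.1 and Section 7.4 of the current protocol

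*Protocol*

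**What the plan says.** All references are to the Amendment 4 text, the last of the protocol versions in the file and the one that SAP Section 2 names as its basis.

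**Stopping at 30 mg.**
- Synopsis, Double-Blind Treatment Period: at the investigator's discretion, "participants unable to tolerate the 30 mg dose may be discontinued from study drug".
- Section 7.1: again at the investigator's discretion, "participants unable to tolerate the 30-mg dose will be discontinued from IP". The same paragraph adds: "Details regarding dose adjustment criteria and procedures are provided in Section 7.4".
- Section 7.4, after a second drug holiday and reduction to 30 mg: "if the events persist or recur and are moderate or severe, the investigator must discontinue the participant from the IP".

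**Events at 45 mg.**
- Synopsis and Section 7.1: the drug holiday is triggered by moderate or severe events, and also when participants "experience these events at any severity with associated symptoms such as confusion or balance impairment, they must have a dose interruption" (7.1 wording; the Synopsis is equivalent). The Synopsis continues: "Following a drug holiday, the dose of study drug must then be reduced by 15 mg decrements to tolerability", and lists 60, 45 and 30 mg. Section 7.1 says the same.
- Section 7.4, first paragraph: it carries both triggers, on Day 1 or at any later point in treatment, and then says "The drug holiday must be followed by reducing the dose of IP from 60 mg to 45 mg".
- Section 7.4, second paragraph: the step from 45 to 30 mg opens with "If the events persist and continue to be moderate or severe, despite the drug holiday and dose reduction", and otherwise needs a new moderate or severe event.
- Section 10.5: it repeats both triggers and says the dose must be adjusted under the 7.4 criteria.

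**The concern.** This is a participant-safety rule, and a site should find the same instruction wherever it looks. At 30 mg the verb moves from *may* to *will* to *must*. The trigger also moves, from a judgement that the dose is not tolerated to a graded criterion. Section 5.2 already lists somnolence as an adverse drug reaction, most doses are taken at home, and Section 12.1.9 allows dose-reduction instructions to be given by telephone. The situation is therefore foreseeable, and much of the handling falls to site staff working from the written rule.

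The practical risk is that sites apply the rule differently. A participant could be stopped at one site and continued at another in the same circumstances, and the second site would be out of line with 7.4 while following the Synopsis.

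**Working it through.** There is no statistic to recompute, so the check is a comparison of texts using one test case per dose.

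**Step 1: figures.** Section 7.4 gives 4, 3 and 2 tablets of 15 mg: 4 × 15 = 60, 3 × 15 = 45, 2 × 15 = 30 mg. These agree with the doses stated elsewhere. The problem is in wording and triggers only.

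**Step 2: 30 mg.**

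| Place | Trigger | Discretion stated | Verb | Points to 7.4 |
|---|---|---|---|---|
| Synopsis | cannot tolerate 30 mg | yes | may | no |
| 7.1 | cannot tolerate 30 mg | yes | will | yes |
| 7.4 | moderate or severe events that persist or recur | no | must | – |

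Section 10.5 has no stopping sentence of its own; it sends the reader to 7.4 for dose adjustment.

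Test case: a participant at 30 mg, after the second holiday, has recurrent moderate somnolence, and the investigator is inclined to continue.
- Under the Synopsis, continuing is open. Either the investigator judges the dose tolerated, so the sentence is not triggered, or it is triggered and *may* leaves the choice.
- Under 7.1, the answer depends on whether the discretion attaches to the judgement of tolerance or to the act of stopping.
- Under 7.4, the investigator has to stop IP.

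Continuing is consistent with the Synopsis and inconsistent with 7.4. Stopping is consistent with all three.

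**Step 3: 45 mg.** Test case: a participant at 45 mg has somnolence graded mild, with balance impairment.

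| Question | Synopsis and 7.1 | 7.4 | 10.5 |
|---|---|---|---|
| Drug holiday? | required | first paragraph can be read as requiring it | defers to 7.4 |
| Reduction from 45 to 30 mg? | described, by decrements guided by tolerability | not named for this case; the second paragraph covers moderate or severe events only | dose must be adjusted, per 7.4 |

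The holiday can be read consistently across all sections. The reduction cannot: 10.5 says an adjustment must follow 7.4, and 7.4 supplies no matching step from 45 mg.

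**Step 4: analysis.** SAP 8.2.6 and 8.2.7 compute exposure and adherence from doses actually taken and the dates on each dose level. Under SAP 7.3 a participant who stops IP stays in the Full Analysis Set if there is a baseline and at least one postbaseline efficacy assessment. No formula depends on which wording a site follows. Stopping status does feed two outputs: the tabulation of TEAEs leading to treatment discontinuation (SAP 8.4.1), and the sensitivity analysis that imputes the worst postbaseline value for missing data after termination for an adverse event or physician decision (SAP 8.3.3.1.3). Uneven application could change who falls into those categories.

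**The case against.** The case against has real weight.

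- **The triggers differ.** Discretion over a broad condition (not tolerating 30 mg) can coexist with an obligation for a narrower one (persisting or recurring moderate or severe events). That is a possible explanation, but the two conditions overlap, and in the overlap the Synopsis and 7.4 still give different strengths.
- **Section 7.1 need not contradict itself.** Discretion may attach to the judgement of tolerance and *will* to its consequence. This stands, and it is one reason why the main conflict lies between the Synopsis and 7.4.
- **Section 7.4 looks like the governing text.** Sections 7.1 and 10.5 refer to it, and it describes its own rules as a minimum. This also stands, but the Synopsis paragraph has no such pointer and no precedence clause exists.
- **At 45 mg, 7.4 is silent rather than contrary.** Its holiday clause runs throughout treatment, and its closing line says the investigator will go on instituting further measures where clinically appropriate, which is more than permission. The Synopsis and 7.1 tie the reduction to tolerability, so a second step is not plainly unconditional there either. The affected group may be small: Section 12.2.5 defines mild events as not affecting performance or functioning, so confusion or balance impairment may often lead to a moderate grade, where the sections agree at 45 mg.

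A reader might infer that Administrative Letter #1 is a further conflicting text. The documents do not support that: it announces an upcoming amendment, and at 30 mg it uses *must*, as 7.4 does. It also opens a rule for events of any severity with confusion or balance impairment, but that instruction is cut off in the supplied text, so nothing can be drawn from it for the 45 mg case.

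**Conclusion.** The 30 mg point holds with high confidence: one stopping decision appears at three strengths in the version in force, and the Synopsis leaves open a course that 7.4 closes. The 45 mg point is secondary and less certain. It is limited to the uneven statement of the 45-to-30 mg reduction for mild events with confusion or balance impairment.

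Two stronger readings should be resisted. A reader might infer that the sections are mutually exclusive and a site cannot comply with all of them. They are not: at 30 mg, stopping satisfies every section, and at 45 mg a holiday followed by reduction does. A reader might also infer that the primary analysis is compromised, but no formula or analysis-set definition turns on the wording.

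The documents give no rate for either situation, so the number of participants affected cannot be stated. The conclusion assumes that some sites would act on the Synopsis or another single section without following the cross-references. It should be corrected, as a wording defect in a safety rule rather than a numerical error.

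**What to change.** Reconcile the Synopsis (Double-Blind Treatment Period) and Sections 7.1, 7.4 and 10.5 so that, at each dose step and at 30 mg, the trigger and the strength of the obligation (mandatory or discretionary) are the same everywhere. This includes the clause on events of any severity with confusion or balance impairment. Check the result against the complete Administrative Letter #1. Which rule applies is for the sponsor's clinical team to decide; this review takes no position on it.

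The cost is a protocol clarification letter or a small amendment touching four places. No analysis needs to change.
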